7.4.2.8 Additional Analyses of the Key Secondary Endpoints

In addition to the main estimates cited in Sections 7.4.2.1 to 7.4.2.7, descriptive supportive estimates for each type of ESA treatment (darbepoetin alfa and epoetin alfa) will be presented for the primary analysis of all key secondary endpoints.

Each of these key secondary endpoints will also be analyzed by the subgroups of interest defined in Section 7.8, using only the primary analysis method.

Forest plots will be produced where all subgroup factors will appear in the y-axis and the appropriate statistic comparing roxadustat to ESA and the 95% confidence interval will appear in the x-axis.

Table 25 Additional Analyses of the Key Secondary Endpoints

Code	Analysis sets	Endpoint	Method	Covariates
A1	PPS	Hb response defined as mean Hb during weeks 28 to 36 within the target range of 10.0 to 12.0 g/dL without having received rescue therapy within 6 weeks prior to and during this 8-week evaluation period by Subgroup	MN method	Region, History of CV, Previous ESA treatment, BL Hb (categorical)
A2	FAS	Change from BL in Low Density Lipoprotein (LDL) cholesterol to the average LDL cholesterol of weeks 12 to 28 by Subgroup.	MMRM	Region, History of CV, Previous ESA treatment, Visits and Visit by Treatment, BL Hb, BL LDL
A3	FAS	Mean monthly IV iron use (mg) during day 1 to week 36 (monthly defined as a period of 4 weeks) by Subgroup.	ANCOVA	Region, History of CV, Previous ESA treatment, BL Hb
A4	PPS	Change from BL in SF-36 Physical Functioning (PF) sub-score to the average PF sub-score of weeks 12 to 28 by Subgroup.	MMRM	Region, History of CV, Previous ESA treatment, Visits and Visit by Treatment, BL SF-36 PF subscore, BL Hb
A5	PPS	Change from BL in SF-36 Vitality (VT) sub-score to the average VT sub-score of weeks 12 to 28 by Subgroup.	MMRM	Region, History of CV, Previous ESA treatment, Visits and Visit by Treatment, BL SF-36 VT subscore, BL Hb
A6	PPS	Change from BL in mean arterial pressure (MAP) to the average MAP value of weeks 20 to 28 by Subgroup.	MMRM	Region, History of CV, Previous ESA treatment, Visits and Visit by Treatment, BL Hb, BL MAP

Table continued on next page

Code	Analysis sets	Endpoint	Method	Covariates
A7	PPS	Time to an increase in blood pressure: An increase from BL of ≥ 20 mm Hg systolic blood pressure (SBP) and SBP ≥ 170 mmHg or an increase from baseline of ≥ 15 mmHg diastolic blood pressure (DBP) and DBP ≥ 100 mmHg during weeks 1 to 36 by Subgroup.	Cox regression	Stratified on Region, History of CV, Previous ESA treatment, and adjusted on BL Hb as continuous covariate
A8	FAS	Change from BL in mean arterial pressure (MAP) to the average MAP value of weeks 20 to 28 by Subgroup.	MMRM	Region, History of CV, Previous ESA treatment, Visits and Visit by Treatment, BL Hb, BL MAP
A9	FAS	Time to an increase in blood pressure: An increase from BL of ≥ 20 mm Hg systolic blood pressure (SBP) and SBP ≥ 170 mmHg or an increase from baseline of ≥ 15 mmHg diastolic blood pressure (DBP) and DBP ≥ 100 mmHg during weeks 1 to 36 by Subgroup.	Cox regression	Stratified on Region, History of CV, Previous ESA treatment, and adjusted on BL Hb as continuous covariate

7.4.3 Analysis of Additional Secondary Efficacy Endpoints

All the analyses below will be superiority tests. These inferential analyses will be performed on the FAS and present the treatment effect of Roxadustat versus ESA.

The analyses will be performed on the total population.

Descriptive statistics will be presented by treatment arm and type of ESA treatment, when applicable.

7.4.3.1 Hb response regardless of use of rescue therapy.

This analysis is identical to the one defined in Section [7.4.2.1](#) except that it is regardless of rescue therapy and a superiority test will be performed on the FAS.

The two-sided 95% CI for the difference in rates will be calculated similarly. If the resulting lower bound of the two-sided 95% CI between roxadustat and ESA is > 0 , superiority will be concluded.

Hb responses (defined as mean Hb values between 10.0 to 12.0 g/dL and also defined as mean Hb values ≥ 10.0 g/dL) during weeks 28 to 36, and during weeks 28 to 52 will be analyzed similarly.

For Hb response (mean Hb between 10.0 to 12.0 g/dL) during weeks 28 to 52 will be analyzed using logistic regressions too, the odds ratio (roxadustat vs. ESA) and their 95% confidence intervals will be produced, if convergence achieved.

The SAS procedure will be similar to the following:

```
proc logistic;  
class treatment previous_ESA_treatment region CV_history;  
model response = treatment previous_ESA_treatment region cv_history  
baseline_Hb;  
run;
```

7.4.3.2 Hb change from BL to each post-dosing time point.

Hb value and change from BL Hb to each post dosing time point will be described by treatment arm on the FAS.

The analysis will be similar to the one provided in Section [7.4.1.1.1](#)

7.4.3.3 Hb level averaged over weeks 28 to 36, 44 to 52, and 96 to 104 without use of rescue therapy within 6 weeks prior to and during these 8-week evaluation periods.

Averaged Hb over weeks 28-36, 44 to 52 and 96 to 104 will be described by treatment arm on the FAS.

The analysis will be similar to the one provided in Section [7.4.1.1.1](#)

In addition, the number and proportion of subjects with average Hb over weeks 28-36 and over weeks 44-52, 72-80 and 96-104 and by visit within the <10 g/dL, >=10 g/dL, 10-12 g/dL and >12 g/dL categories will be reported.

7.4.3.4 Hb change from BL to the average Hb value of weeks 28 to 36, 44 to 52, and 96 to 104 regardless of the use of rescue therapy.

The analysis will be done similarly as in Section [7.4.1.1.1](#) on the FAS except that it will be for weeks 28-36, 44-52 and 96-104.

7.4.3.5 Categorical analysis for Hb values

For the analyses below, results will be displayed by treatment arm and type of ESA treatment.

Proportion of Hb values:

The proportion of Hb values >=10 g/dL and within 10-12 g/dL is a quantitative variable in the 0 – 100 range for each subject. Descriptive statistics for this variable will be presented. This variable will be presented in weeks 28-36, in weeks 44-52 and in weeks 96 -104, on the FAS.

Percentage of time during the Efficacy Emergent Period:

Descriptive statistics for the percentage of time with Hb values falling in each interval (<10.0 g/dL, >=10 g/dL, within 10.0-12.0 g/dL, > 12.0 g/dL, > 13.0 g/dL and > 14.0 g/dL) between the first and last Hb assessment during the Efficacy Emergent Period will be presented.

The number and percentage of subjects, and the number of events, will be reported by for the following potential EH events of interest, based on Hb values from the central laboratory:

- Hb increase by >2.0 g/dL between any two visits within 4 weeks of treatment

Time to first occurrence of potential EH will also be analyzed similarly as in Section [7.4.2.7](#) (except that all data during the Efficacy Emergent Period will be taken into account for the analysis).

Subjects with at least one Hb value > 13 g/dL during the treatment period will be summarized.

7.4.3.6 Occurrence (number) of hospitalizations, number of days of hospitalization per year and time to first hospitalization during the study.

The number and percentage of subjects with hospitalization will be reported. Descriptive statistics and frequency tabulations by treatment arm and type of ESA treatment of the total duration of hospitalization (days), the average duration of each hospitalization (days), the number of hospitalizations, number of days of hospitalization per year and reason for hospitalization will also be reported.

Time to first hospitalization will also be analyzed similarly as in Section [7.4.2.7](#) (except that all data during the Efficacy Emergent Period will be taken into account for the analysis).

Superiority will be declared if the upper bound of the two-sided 95% confidence interval of the hazard ratio of the two treatment arms is below 1.

The analysis will be done on the FAS.

7.4.3.7 Occurrence and time to first use of rescue therapy, occurrence and time to first use of RBC transfusions, number of RBC packs per subject, volume of RBC transfused per subject.

The number and percentage of subjects with rescue therapy will be reported by treatment arm and type of ESA treatment. Time to first use of rescue therapy will also be analyzed similarly as in Section [7.4.2.7](#) (except that all data during the Efficacy Emergent Period will be taken into account for the analysis).

Mean monthly number of RBC packs and volume of RBC transfused during the Efficacy Emergent Period will be compared by treatment arm using an ANCOVA model as in Section [7.4.1.2.1](#). Subjects with no medication record of RBC will be assumed that they received no RBC and therefore number of packs and volume will be set to 0.

The analysis will be done on the FAS.

Superiority will be declared if the upper bound of the two-sided 95% confidence interval of the hazard ratio of the two treatment arms is below 1.

In addition, the number and percentage of subjects with RBC transfusion will be reported. Descriptive statistics by treatment arm and type of ESA treatment for number of RBC packs and volume of blood transfused will be reported. Time to first use of RBC transfusion will be analyzed similarly as in Section [7.4.2.7](#) (except that all data during the Efficacy Emergent Period will be taken into account for the analysis).

The number and percentage of roxadustat subjects with ESA use as rescue therapy, and the number of ESA-weeks will be reported descriptively for the roxadustat treatment arm only.

7.4.3.8 Occurrence of iron supplementation.

The number and percentage of subjects who received IV Iron and the total amount of IV Iron used during the study will be reported descriptively by treatment arm and type of ESA treatment.

The incidence and cumulative incidence of subjects receiving IV Iron will be calculated similarly as in Section 7.4.2.7 (except that all data during the Efficacy Emergent Period will be taken into account for the analysis).

Mean monthly IV iron (mg) per subject during weeks 37-52 and weeks 53-104 will be compared by treatment arm and analyzed similarly as in Section 7.4.2.3

The analysis will be done on the FAS.

7.4.3.9 Change from BL to each post-dosing study visit in Total cholesterol, LDL/High-density Lipoprotein (HDL) ratio, Non-HDL cholesterol, Triglycerides, Apolipoproteins A1 and B, ApoB/ApoA1 ratio.

Descriptive statistics (value, change from baseline) by visit, treatment arm and type of ESA treatment will be presented regardless of fasting status, including averages in week 12-28. Descriptive statistics will also be reported with fasted values.

7.4.3.10 Occurrence of mean LDL cholesterol <100 mg/dL calculated over weeks 12 to 28.

The number and percentage of subjects with mean LDL cholesterol less than 100 mg/dL (2.59 mmol/L) (regardless fasting status) on average in weeks 12-28 will be reported by treatment arm and type of ESA treatment. Descriptive statistics and frequency tabulations will also be reported on fasted values, and regardless of fasting status.

7.4.3.11 Occurrence of achieved antihypertensive treatment goal in CKD subjects (SBP < 140 mmHg and DBP < 90 mmHg) based on the mean SBP and mean DBP calculated over weeks 12 to 28.

The number and percentage of subjects with achieved antihypertensive treatment goal over an evaluation period defined as the average of available values in weeks 12-28 will be reported by treatment arm and type of ESA treatment.

7.4.3.12 Health related Quality of Life Questionnaires Change from BL to the average value of weeks 12 to 28

The following questionnaires will be analyzed:

- SF-36 (Physical Component Score (PCS));
- FACT-An (Anemia Subscale (“Additional Concerns”), Total FACT-An Score);
- EQ-5D 5L (VAS Score);
- Patients’ Global Impression of Change (PGIC).

SF-36 and FACT-An

Descriptive statistics and frequency tabulations (value, change from baseline) will be presented for SF-36 (subscale and component scores) and FACT-An (total and subscale scores) by visit, treatment arm and type of ESA treatment. Mean values will also be plotted over time and by treatment arm.

In addition, for the average value in weeks 12-28, an inferential analysis, similar to the one defined in Section 7.4.1.1.1 will be performed for the following endpoints:

- Physical Component Scores of SF-36 (SF-36 PCS)
- Anemia Subscale (“Additional Concerns”) of FACT-An Scores
- Total FACT-An Scores
- Fatigue

For SF-36, at each visit, the frequency and proportion of subjects with a change from baseline ≤ 3 points and ≤ 5 points will be reported for Physical Functioning, Vitality and Physical Component scores.

In addition to this, change from BL to the average value of weeks 36 to 52 will be summarized similarly as for change from BL to the average value of week 12 to 28.

EQ-5D 5L

For the EQ-5D 5L VAS score, change from baseline to each visit and to the average of weeks 12-28 and 36-52 will be described by treatment arm.

For the 5 EQ-5D 5L qualitative domains, the number and percentage of subjects in each response level value will be reported by visit, treatment arm and type of ESA treatment.

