##### *Hospitalizations:*

- Occurrence (number) of hospitalizations (HD days are not counted as hospitalizations, even when performed overnight).
- Number of days of hospitalization.

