#### **7.4.3 Analyses of Additional Secondary Endpoints**

The statistical analyses of the additional secondary endpoints will be detailed in the SAP.

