In case that several Hb values are on the same day the average of these values will be used to represent the Hb of that day in the above formula. This calculation will provide the day that the change in Hb value occurs. The number of days that the Hb value has been in each category will be determined and the percentage calculated based on the length of time between the first and last Hb assessment during the evaluated period, i.e.:

Date of Last Hb assessment during the evaluated period – Date of first assessment during the evaluated period.

No imputation will be performed if no Hb value is available in relevant time windows.

In case a subject requires rescue therapy within 6 weeks prior to and during these 8-week evaluation periods, refer to Section 7.11.1 for imputation rules.

Potential Excessive Hematopoiesis (EH), regardless use of rescue therapy, based on Hb central laboratory

The presence of potential EH will be defined as:

- Hb increase by >2.0 g/dL between any 2 visits within 4 weeks of treatment

Time to first occurrence of potential EH regardless the use of rescue therapy during the treatment period will be defined in weeks as:

$$(\text{First event date} - \text{Analysis date of first dose} + 1) / 7$$

where ‘First event date’ is defined as first date of occurrence of the criterion met during the treatment period.

For a subject without potential EH, the time to censoring will be calculated (in weeks) as:

$(\text{Min}(\text{Date of last hemoglobin assessment during the Efficacy Emergent Period, End Date of the Efficacy Emergent Period}) - \text{Analysis date of first dose} + 1) / 7$

Refer to Section [7.11.6](#) for the definition of the Efficacy Emergent Period.

6.1.3.6 Occurrence (number) of hospitalizations, number of days of hospitalization per year and time to first hospitalization.

The occurrence and the number of non-HD hospitalizations per subject during the Efficacy Emergent Period will be calculated. HD days are not counted as hospitalizations, even when performed overnight.

The number of days of hospitalization per year treated will be calculated as:

$[\text{Sum of the durations of all non-HD hospitalizations in days (Date of discharge} - \text{Date of admission} + 1)] / (\text{duration of efficacy emergent period in days} / 365.25)$.

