Version	Date	Changes	Comment/rationale for change
		
submission (change in Hb from baseline to the average level between week 28 and week 52) with the description of the statistical analyses including sensitivity analyses for missing data.
 
13) Interim analysis changed from week 36 to week 52.
 
14) Implementation of time to first hospitalization and time to first potential EH .
 
15) Update regarding the analysis on cholesterol data: use of all data as main analysis and fasted only as additional..
 
16) Reduction in the number of analyses of subgroup of interests.
 
17) Addition of the analysis of percentage of time when Hb > 12, 13 or 14.
 
18) MMRM model added for number of RBC and volume of RBC during the treatment period.
 
19) Removal of descriptive analysis on the categorical change form baseline in Total FACT-An Score.
 
20) Addition of an analysis on a subset of subjects with baseline PF subscore <40 and ≥40, and baseline VT subscore <50 and ≥ 50.
 
21) Updated rule for complete missing start date and end date for concomitant medications. In that case, the medication will be considered as both previous and concomitant instead of only concomitant.
 
22) For the analysis of monthly IV Iron use, MMRM has been replaced by ANCOVA.
 
23) Additional tables run on group of subjects enrolled after protocol
	
been added in protocol amendment 1.0.Sensitivity analyses for missing data were added following FDA feedback on the Fibrogen 064 study.
 
13) This has been changed in protocol amendment 1.0.
 
14) Due to harmonization with Fibrogen 064 study SAP and the expected difference in treatment durations
 
15) Due to the assumption that most samples were not taken fasted and harmonization with Fibrogen 064 study SAP.
 
16) To limit the total number of analyses and the volume of tables
 
17) The concept of percentage of time with high Hb values was implemented in order to account for differences in individual treatment durations.
 
18) Inferential analysis for RBC was missing in the v1.0.
 
19) Descriptive statistics for categorical change not necessary since analysis on absolute change already planned and considered sufficient.
 
20) Due to harmonization with Fibrogen 064 study SAP.
 
21) Previous rule considered too conservative since a missing year of start is usually for previous medications than concomitant. Decision was taken to consider such medications as both previous and concomitant.
 
22) MMRM model for monthly IV Iron was not adapted due the data distribution. Since monthly average will be calculated, ANCOVA is more appropriate.
 
23) Added in order to assess the

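### The number of hospitalizations has no between-arm comparison in the SAP; the only hospitalization test is time to first admission, which makes no use of repeat admissions

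*SAP*

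**What the plan says.** Protocol 2.3.3.1 names two hospitalization endpoints: "Occurrence (number) of hospitalizations (HD days are not counted as hospitalizations, even when performed overnight") and "Number of days of hospitalization". It gives no method for either. Protocol 7.4.3 leaves that open: "The statistical analyses of the additional secondary endpoints will be detailed in the SAP".

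SAP 6.1.3.6 derives the count: "The occurrence and the number of non-HD hospitalizations per subject during the Efficacy Emergent Period will be calculated". It divides days of hospitalization by the length of the Efficacy Emergent Period, but specifies no such scaling for the number of admissions. It also defines time to first hospitalization, which the protocol does not list.

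SAP 7.4.3 opens by calling every analysis under it a superiority test on the FAS. In 7.4.3.6, however, the count and the days get descriptive statistics and frequency tables: "the number of hospitalizations, number of days of hospitalization per year and reason for hospitalization will also be reported". The only model is for the first admission ("Time to first hospitalization will also be analyzed similarly as in Section" 7.4.2.7), and the only decision rule follows from it: superiority is claimed when the upper 95% limit for that hazard ratio lies under 1.

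The SAP revision history (version 2.0, item 14) explains why time to first hospitalization was brought in: "Due to harmonization with Fibrogen 064 study SAP and the expected difference in treatment durations".

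**The concern.** In a first-event analysis, a subject admitted once and a subject admitted six times within the same follow-up contribute one event each. The endpoint the protocol names is the number, and for that number the SAP specifies no test, rate ratio or confidence interval.

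The descriptive table is a weak substitute. Treatment lasts between 52 and 104 weeks, and SAP 7.5.1.4 itself warns that adverse event percentages may differ between arms because discontinuation rates differ. A raw count per subject has the same problem, and only the days are put on a per-year scale.

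The SAP handles the neighbouring endpoint differently. Under 7.4.3.7 the number of RBC packs is compared between arms as well as time to first transfusion. Item 18 of the version 2.0 changes says that model was added because an inferential analysis had been missing. Hospitalization received only the time-to-first half.

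At stake is precision on hospital burden in a dialysis population: a difference in repeat admissions would show in the tables without an interval by which to judge it.

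**Working it through.** **The plan's own figures.** None is given for hospitalization. The only power statements concern the two Hb primary endpoints. The EU one reproduces: distance to margin 0.75 − 0.25 = 0.50 g/dL, SD 1.5, 300 per arm, one-sided alpha 0.0174. SE = 1.5 × √(2/300) = 0.1225, and power = Φ(0.50/0.1225 − 2.11) = 97.6%, against the stated 97%. This says nothing about admissions.

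**Inputs from the documents.** About 750 subjects randomized 1:1, so 375 per arm; treatment for 52 to 104 weeks; two-sided 95% CI as the decision rule.

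**Inputs assumed.** Control admission rate r per year, rate ratio RR, between-subject (gamma) variance k, common follow-up T in years.

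**Count model (negative binomial, Wald test on log RR).** Variance = [1/(T·r) + 1/(T·r·RR) + 2k]/n, and power = Φ(|ln RR|/SE − 1.96).

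- r = 0.5, k = 1, T = 1, RR = 0.80: (2.0 + 2.5 + 2.0)/375 = 0.01733, SE 0.1317, 0.2231/0.1317 = 1.695, power 39.5%.
- r = 1.5, k = 0.5, T = 1.5, RR = 0.80: (0.444 + 0.556 + 1.0)/375 = 0.00533, SE 0.0730, 0.2231/0.0730 = 3.056, power 86.3%.

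**First-event test (log-rank) under the same process.** In the control arm S0(t) = (1 + k·r·t)^(−1/k) and h0(t) = r/(1 + k·r·t); the roxadustat arm uses r·RR. With w = n·S0·S1/(S0 + S1), drift U = ∫w(h0 − h1)dt and variance V = ∫w(h0·S0 + h1·S1)/(S0 + S1)dt over 0 to T. Power = Φ(U/√V − 1.96).

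- First case: U = 10.93, V = 58.0, U/√V = 1.435, power 30.0%.
- Second case: U = 24.37, V = 140.3, U/√V = 2.058, power 53.9%.

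In the first case the average first-event hazard ratio is about exp(−10.93/58.0) = 0.83, although the true rate ratio is 0.80. The highest-risk subjects leave the risk set first, which pulls the hazard ratio toward 1.

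| Rate per year | k | Years | Count model | First event | Gain (points) |
|---|---|---|---|---|---|
| 0.5 | 0.5 | 1 | 45.3% | 36.1% | 9.2 |
| 0.5 | 1 | 1 | 39.5% | 30.0% | 9.6 |
| 1.0 | 1 | 1 | 55.4% | 36.0% | 19.4 |
| 1.5 | 2 | 1.5 | 48.9% | 23.8% | 25.1 |
| 1.5 | 0.5 | 1.5 | 86.3% | 53.9% | 32.4 |

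All rows have RR = 0.80 and 375 per arm; gains are taken before rounding.

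**Checks by simulation.** With planned follow-up uniform over 1 to 2 years, discontinuation 0.2 per year, RR 0.80, rates 0.5 to 1.5 and k 0.5 to 2, the gain ran from 9 points (31% against 22%) to 33 points (82% against 49%). That used 400 trials per cell, so each power carries a standard error of about 2.5 points. Under no effect the one-sided error rate was 2.3% for the count model and 1.8% for the first-event test (600 trials), so both tests are valid. A second simulation, with k from near 0 to 2 and rates up to 2.0 per year, gave gains of 7.2 to 36.3 points, with 19% to 78% of admissions being repeats.

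**Wider inputs.** With RR 0.70 to 0.90, rate 0.3 to 2.0, k 0.5 to 2 and follow-up 1 to 2 years, the gain is 1.2 to 40.6 points. Letting k run from 0 to 3 gives 0.3 to 50.5. Small gains can arise where neither test has much power: at RR 0.90, rate 0.3, k 0.5 and 1 year, the variance is (3.33 + 3.70 + 1)/375 = 0.0214, z = 0.1054/0.1464 = 0.72, and the count model itself has only about 11%. The gain was positive in every cell.

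**The case against.** Time to first event is a standard and valid analysis. The protocol promises no test of the count and leaves the method to the SAP, and the SAP keeps both protocol endpoints and adds a third. The endpoint sits outside the nine-test fixed sequence and was never powered. All of this stands, and it limits the point to an improvement.

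Three stronger readings are tempting, and the documents do not support them.

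- *That repeat admissions are thrown away.* They are not. The count, total days, days per year and reasons are derived and reported by arm, so a difference could be seen. What is missing is a model and an interval.
- *That the SAP cut a count test and gave a poor reason.* Item 14 explains an addition. Nothing available shows that a comparison of counts was ever planned and removed. It is still true that unequal treatment durations, one of the two reasons given there, would be met equally well by a count model with an offset.
- *That a fixed amount of power is lost.* Every rate, dispersion and effect used above is assumed. The calculation also uses an unadjusted log-rank test, whereas the SAP's Cox model is stratified on three factors and adjusted for baseline Hb, and it ignores death as a terminal event.

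A count model has its own weakness. SAP 6.1.3.6 merges two hospital records only when one admission date equals the previous discharge date, so other split records count as separate admissions. The date of first admission is far less sensitive to this.

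**Conclusion.** The point holds as a low-cost improvement. The number of hospitalizations is a named endpoint that the SAP derives but does not compare between arms or scale for follow-up, and the one hospitalization test makes no use of repeat admissions. The direction of the cost is firm under the gamma-Poisson model with constant rates and one common rate ratio. Its size is not: roughly 9 to 33 points at a rate ratio of 0.80 with 0.5 to 1.5 admissions per year and heterogeneity variance 0.5 to 2, and about 1 to 41 points over wider inputs. Primary and key secondary conclusions are untouched, and no planned power is lost. Days of hospitalization likewise have no between-arm comparison.

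**What to change.** In SAP 7.4.3.6, add a between-arm comparison of the number of non-HD hospitalizations on the FAS. Use a negative binomial model with treatment, region, CV history, previous ESA treatment and baseline Hb as terms and the log of the Efficacy Emergent Period in years as offset, and report the rate ratio with its 95% CI. Keep the Cox analysis of time to first hospitalization so that the result harmonized with the sister study remains available.

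The cost is a paragraph of SAP text and one model on variables that SAP 6.1.3.6 already derives. There are two limits to state with it. The count depends more than the first-admission date on how split records are merged. And, like the Cox censoring, the model assumes that stopping or death is unrelated to admission risk given the covariates. SAP section 1 allows revision before hard lock; after that, the addition would have to be justified in the study report.
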